7.2. Secondary Endpoint Analyses

Secondary endpoints included in the analysis are composite endpoints of post-randomization infectious complications (wound infections, pneumonia, and sepsis) at 90 days and cardiac complications (new cardiac arrhythmia, new or worsening CHF, and cardiac arrest not leading to death) at 90 days, all-cause mortality at one year after randomization, a composite endpoint of all-cause mortality, MI, coronary revascularization, acute renal failure, or post-randomization ischemic stroke at 30 days, and length of hospital stay after randomization.

For the binary endpoints, the effect of transfusion strategy on these endpoints will be analyzed initially with a Pearson chi-square test (Tables 18a-e) and additional analysis will be performed by taking account of age, RCRI, and nadir Hb using logistic regressions (Tables 19a-e), as described in the primary endpoint analysis.

For the length of hospital stay after randomization, medians (interquartile ranges) will be presented, and Wilcoxon rank sum test will be used to compare the medians of the length of hospital stay between the two intervention groups (Tables 20a-e) using PROC NPAR1WAY. In addition, quantile regression model will be performed using PROC QUANTREG to test the effect of the intervention on the time until discharge from hospital adjusted for age, RCRI, and nadir Hb (Tables 21a-e), as described in the primary analysis. The test for differences between transfusion strategies in each secondary outcome will be conducted at an α -level of 0.01. The

analyses will be done in the ITT, mITT, No-Recent-Transfusion, Completers, and Per Protocol populations.

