Outcome 4: A composite endpoint of all-cause mortality, MI, coronary revascularization, acute renal failure, or post-randomization stroke at 30 days after randomization.

Outcome 5: Length of hospital stay after randomization.

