4.5. Sample Size Consideration

The sample size estimation and power analysis are based on the hypothesis testing of the primary composite endpoint of all-cause post-randomization mortality, myocardial infarction (MI), coronary revascularization, acute renal failure, or post-randomization stroke up to 90 days after randomization. The primary hypothesis of the study is that in VA patients with high cardiac risk undergoing a surgical procedure, a significantly smaller proportion of participants receiving blood under a liberal transfusion strategy will experience the composite endpoint compared to participants under restrictive transfusion strategy at 90 days after randomization. The primary analysis will be done as an "intent-to-treat" analysis. Our database review revealed that 29.8% out of 25,343 patients in the VA population who were at high cardiac risk and had nadir postoperative Hb range between 6-9 gm/dl developed the composite endpoint of death, MI, acute renal failure, or coronary revascularization within 90 days from the index operation. Based on the analysis, a baseline event rate of 30% for the composite endpoint is expected in the restrictive group. We also assume a 25% reduction or 22.5% event rate in the liberal group. To detect the expected 7.5 percentage point difference or 25% reduction, a sample size of 1444 will be required at 90% power, 5% type-I error rate and with a two-sided test (Appendix 3). Assuming 5% dropout rate, then 1520 participants (or 760/group) will be needed to achieve the desired testing power.

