5.2. Missing Data and Imputations

Every effort will be made to minimize the occurrence of missing data, particularly for the primary and main secondary outcome measures. For the primary outcome, every effort will be made to contact participants until subject termination. In the event of a potential drop out, every effort will be made to capture the primary outcome data from the VA databases. For participants who drop out during the study multiple imputation (MI) method may be used for certain endpoint analyses. Multiple imputations will be based on Rubin's procedure using SAS PROC MI and PROC MIANALYZE when missing is at random. Sensitivity analysis will be performed to compare the results from the imputed data and the complete data without imputation.

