5.4. Analysis Populations

Intent-to-Treat (ITT) – This population is defined as the population of participants (except non-Veterans and previous participants of this trial) who will be randomized to either of the transfusion strategy groups – Liberal or Restrictive. The participants will be categorized (in terms of their transfusion strategy assignment) based on their initial randomized group and will be included in analyses irrespective of their status – completer or drop out of the study before completion. The testing power for the primary endpoint is estimated as 90% in this population.

Modified Intent-to-Treat (mITT) – This population is defined as a subset of the ITT population that excludes randomized participants in a justified way, i.e., participants who are found to be ineligible (violating inclusion/exclusion criteria) or participating in more than one simultaneous intervention trial.

No-Recent-Transfusion – This population is defined as a subset of the ITT population excluding the participants who will receive transfusions within 30 days prior to or during the index operation, or after the index operation but before randomization.

Completers – This population includes all ITT participants who will complete all protocol-required lab and EKG assessments, hemoglobin monitoring and transfusion records in the hospital stay or until death, as well as completing assessments of the 5 individual components of the primary endpoint at 30 day and 90-day follow-up or until death.

Per Protocol – This population includes all ITT participants who will adhere to transfusion protocol in their assigned intervention groups.

Safety – This population includes all participants (except non-Veterans and previous participants of this trial) who will be randomized to either of the transfusion strategy groups – Liberal or Restrictive.

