7.4. Other Analyses

Age of blood in relation to 90-day composite endpoint, wound infection, and pneumonia

Analyses will be conducted of the associations between characteristics of transfused blood and three outcome measures: 90-day composite endpoint (Tables 24a-e), wound infection (Tables 25a-e), and pneumonia (Tables 26a-e). Current data collection plans call for blood expiration dates and the age of each unit of blood transfused will be calculated. Logistic regression models will be fitted to test for association between these outcomes and age of blood transfused (entered in different models as oldest unit transfused or as mean age of all units transfused). The analyses will be adjusted for baseline age, RCRI, nadir Hb, and the transfusion intervention. The test for differences of these outcomes will be conducted at an α -level of 0.05 for the primary outcome and 0.01 for wound infection and pneumonia. The analyses will be done in the ITT, mITT, No-Recent-Transfusion, Completers, and Per Protocol populations.

Time-to-event analysis for primary and major secondary endpoints

Survival analysis techniques will be used to analyze the time-to-event data for the primary and major secondary endpoints. Kaplan-Meier method will be used to estimate the survival (not experiencing event) over time in the two intervention groups and a log-rank test

will be used to compare the survival functions in the two groups for the primary endpoint and the secondary endpoints using PROC LIFETEST. Cox's Proportional Hazards models will be used to test the effect of the intervention on the time until endpoint events adjusted for age, RCRI, and nadir Hb, as described in the primary endpoint (Tables 27a-e, with an α -level of 0.05), and secondary endpoint (Tables 28a-e, with an α -level of 0.01) analyses using PROC PHREG. The analyses will be done in the ITT, mITT, No-Recent-Transfusion, Completers, and Per Protocol populations.

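### Does the silence on death before discharge, together with a non-fatal cardiac composite, make the secondary comparisons unreliable?

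*SAP*

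**What the plan says.** SAP 3.2.2 defines the endpoint in one line: "Outcome 5: Length of hospital stay after randomization". SAP 7.2 then says "medians (interquartile ranges) will be presented, and Wilcoxon rank sum test will be used to compare the medians of the length of hospital stay", at alpha 0.01, and adds a quantile regression for the "effect of the intervention on the time until discharge from hospital". Table shells 20 and 21 have no row or note for deaths.

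Three other places bear on a participant who dies in hospital, and none assigns a stay:

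- SAP 5.2, missing data: "For participants who drop out during the study multiple imputation (MI) method may be used for certain endpoint analyses". Death is not mentioned.
- SAP 5.4, ITT: participants "will be included in analyses irrespective of their status".
- SAP 5.4, Completers: required items include "hemoglobin monitoring and transfusion records in the hospital stay or until death". This settles who belongs to the set, not what their stay is.

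The cardiac composite counts only arrests that are reversed; an unreversed arrest is classed as a death (Protocol V.B, SAP 3.2.2). Of the log-rank analysis, SAP 7.4 says that it "will be used to compare the survival functions in the two groups for the primary endpoint and the secondary endpoints using PROC LIFETEST"; adjusted models follow (Table 28). The section is silent on whether death censors or competes.

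**The concern.** The trial itself expects deaths to differ: the protocol's secondary and tertiary hypotheses predict fewer under liberal transfusion. If stay simply ends at death, early deaths in the restrictive arm become short stays and count against the hypothesis that liberal transfusion shortens stay. If deaths come late, the bias runs the other way. An unstated rule could also be chosen once the data are known.

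The cardiac composite raises a similar worry. A participant whose only event is a fatal arrest is recorded as having no cardiac complication, so an arm could look better because more of its participants died. The infectious composite has the same structure. At stake is the reading of secondary comparisons, each tested at alpha 0.01.

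**Working it through.** **The plan's own figure.** SAP 4.5 expects 30% in the restrictive arm and says "We also assume a 25% reduction or 22.5% event rate in the liberal group". With a pooled-variance two-proportion formula and no continuity correction:

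n = [1.960·√(2×0.2625×0.7375) + 1.282·√(0.30×0.70 + 0.225×0.775)]² / 0.075² = 721.2, so 722 per arm and 1444 in total. Then 1444/0.95 = 1520. Both figures reproduce, and nothing below alters them.

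**Length of stay: inputs.** From the plan: 760 per arm, two-sided alpha 0.01 (0.5% per direction, z = 2.576). Protocol Table 2 gives 90-day death of 15.3% (nadir Hb 6-9) and 6.9% (9-10). Assumed, because the documents give no values: identical log-normal stays with log SD 0.7; death unrelated to would-be stay; a 25% reduction applied to in-hospital death, so that 15.3% becomes 15.3 × 0.75 = 11.5%. Using 15.3% treats every 90-day death as in-hospital, which is an upper case.

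**Formula.** Let θ be the chance that a decedent's recorded stay exceeds a survivor's. With identical stays in both arms, the Wilcoxon effect P(restrictive stay > liberal stay) − 0.5 equals (θ − 0.5)(d_R − d_L), where d is the proportion dying in hospital. Its null standard error is √[1521/(12 × 760²)] = 0.01481. With σ = 0.7√2 = 0.990:

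- All deaths early (stay is a uniform fraction of would-be stay): θ = 0.5 − e^{0.49}·Φ(−0.990) = 0.237.
- All deaths late (twice would-be stay): θ = Φ(0.693/0.990) = 0.758.
- Half early, half late: θ = (0.237 + 0.758)/2 = 0.498.

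Example, 8% v 6%, all early: (0.237 − 0.5) × 0.02 = −0.00526; divided by 0.01481 this is −0.355; Φ(−2.576 + 0.355) = 1.3% favouring restrictive.

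| Deaths, restrictive v liberal | All early, favours restrictive: formula (simulated) | All late, favours liberal: formula (simulated) | Half and half, favours restrictive/liberal: simulated |
|---|---|---|---|
| 5 v 3.75% | 0.9% (0.7%) | 0.9% (0.7%) | 0.6/0.5% |
| 8 v 6% | 1.3% (1.4%) | 1.3% (1.2%) | 0.4/0.6% |
| 10 v 7.5% | 1.7% (1.8%) | 1.6% (1.6%) | 0.8/0.4% |
| 15.3 v 11.5% | 2.9% (2.7%) | 2.8% (2.8%) | 0.4/0.5% |
| 15 v 7% | 12.4% (12.7%) | 11.9% (12.5%) | 0.5/0.5% |

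The simulations used a median of 8 days, stays rounded up to whole days, and 4000 to 5000 trials. Monte Carlo error near 0.5% is about √(0.005 × 0.995/4000) = 0.1 point.

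An even mix is close to the exact balancing point, so it is a favourable case. With three quarters of deaths early, θ − 0.5 = 0.75 × (−0.263) + 0.25 × 0.258 = −0.133. The same formula gives 0.8% at 8 v 6 and 1.3% at 15.3 v 11.5.

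**Power if liberal transfusion truly shortens stay by 14%.** All early: 83% (8 v 6) and 69% (15.3 v 11.5). Half and half: 91% and 89%. Discharged-alive only: 92% and 89%.

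**What the alternatives cost.** Restricting to those discharged alive stays near nominal only if death is unrelated to would-be stay. If deaths concentrate in long-stay patients, it favours restrictive in 0.8 to 2.4% of trials at a 25% reduction, against 1.4 to 4.3% when early deaths are counted as stays. Ranking death worst favours liberal in 1.6 to 9.8% with identical stays, because it also responds to mortality.

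**Cardiac composite.** Suppose a 15% risk in survivors, equal by arm, and that death pre-empts the event in everyone who dies. The observed rates are then 0.15 × 0.847 = 12.7% and 0.15 × 0.885 = 13.3%, a shift of 0.6 point. With a 25% risk they are 21.2% and 22.1%, a shift of 1.0 point. At the Table 2 contrast (6.9% liberal deaths) the shifts are 1.3 and 2.1 points.

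A companion endpoint of cardiac complication or death dilutes. A 15% v 10% cardiac difference has 65% power at alpha 0.01. Adding independent 10% mortality with no effect gives 1 − 0.85 × 0.90 = 23.5% against 1 − 0.90 × 0.90 = 19.0%, and power of 33%.

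**The case for a change.** The strongest case for a change is that the direction of the stay result depends on a rule nobody has written down. The protocol promises a SAP with the analysis details for each outcome, and a sentence now would close off a choice made after unblinding. The power loss, down to 69%, is more striking than the false-positive rate. Separate mortality tables would show an imbalance without telling a reader whether a lower non-fatal cardiac rate means benefit or more deaths.

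Part of this stands. The rule is absent, and writing it down would do no harm. But the large figures need every decedent to share one timing, and the largest also need all 90-day deaths to occur in hospital. The 15 v 7 contrast resembles the unadjusted observational groups in Protocol Table 2, not a planned effect. The post-hoc choice is between rules that each have a known weakness. Discharged-alive conditions on survival after randomization and leaves the ITT set on which SAP 7 places the secondary endpoints. Worst rank measures mortality as much as stay. No rule is clearly better, so the plan cannot be faulted for missing an obvious one.

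The point about reading a non-fatal cardiac rate is fair, but a merged endpoint does not resolve it, since non-cardiac deaths enter as well.

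**Conclusion.** No change is called for. For length of stay this is a gap analysts can fill sensibly. The stay of a participant who dies in hospital is observed, ending at death, and the Completers wording treats such records as complete; imputation is reserved for dropouts. Under that reading, at mortality differences of the size the plan assumes for its composite, the excess is about 0.2 to 2.4 percentage points over the nominal 0.5% per direction with uniform timing, and close to none with evenly mixed timing. This rests on the assumed stay distribution, death timing and in-hospital share, none of which the documents give. A much larger mortality contrast with all deaths early would distort the result more, but deaths by arm would then be plain from Tables 6, 22 and 30.

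The non-fatal cardiac composite is a deliberate choice, and both documents say where fatal arrests go. Death is compared by arm in the primary composite, in 90-day mortality (Table 22, same alpha, same five populations), in the 30-day composite and in one-year mortality; the last two sit in Table 18 beside the cardiac result. A death-inclusive companion is optional and weak.

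In SAP 7.4, censoring at death is the usual default and gives a recognised comparison of cause-specific hazards, in analyses the plan lists only as other analyses. The primary test and its sample size are untouched.

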3.2.2. Secondary Outcome Variables

There are five secondary outcome measures based on their use in previous studies.

Outcome 1: A composite endpoint of post-randomization infectious complications at 90 days post-randomization: Infectious complications will include wound infections, pneumonia, and sepsis.

Wound infection will be defined according to the Centers for Disease Control and Prevention (CDC) guidelines as a) positive wound culture, or b) drainage of pus from a wound, or c) suspicion of wound infection that was drained operatively.

Pneumonia will be defined according to the CDC definition as chest radiograph or imaging with new or progressive infiltrate, consolidation, cavitation, or pleural effusion and any of the following: new onset of purulent sputum or change in character of sputum, or organism isolated from blood culture, trans-tracheal aspirate, bronchial brushings, or biopsy.

Sepsis will be defined as a combination of two of the following systemic inflammatory response syndrome (SIRS) criteria, plus suspected or present source of infection. SIRS criteria will include the following: temperature greater than 38C, heart rate greater than 90 beats/min, WBC > 12,000 or < 4,000, or > 10% bands.

Outcome 2: A composite endpoint of cardiac complications (other than MI) at 90 days post-randomization: Cardiac complications will include new cardiac arrhythmias that necessitate new treatment, congestive heart failure (CHF) exacerbation, and cardiac arrest.

The diagnosis of cardiac arrhythmias will be based on EKG findings. Only arrhythmias that result in initiation of new treatment regimen (to include medications, implantable devices, or surgical intervention) during hospitalization will be recorded.

CHF will require at least one of the following symptoms or signs new or worsening: dyspnea at rest, orthopnea, or paroxysmal nocturnal dyspnea and radiological evidence of heart failure or worsening heart failure and increase/initiation of established treatment.

Cardiac arrest will be defined as the cessation of cardiac pump function activity that results in loss of consciousness and absence of circulating blood flow as evidenced by absent

carotid pulse. Only episodes of cardiac arrest that are reversed will be collected under this endpoint. If they are not reversed the event will be categorized as death.

Outcome 3: All-cause mortality at 1 year after randomization.

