5.3. Analysis Conventions

This section details general policies to be used for the statistical analyses. Departures from these general policies may be given in the specific detailed sections of this statistical analysis plan. When this situation occurs, the rules set forth in the specific section take precedence over the general policies. The following policies will be applied to all data presentations and analyses.

All statistical tests will use a significance level of $\alpha = 0.05$ unless otherwise specified. Two-tailed tests will be performed for all analyses that use statistical testing.

All p-values will be rounded to 3 decimal places. All p-values that round to 0.000 will be presented as ‘<0.001’ and p-values that round to 1.000 will be presented as ‘>0.999’. Any p-value $\leq \alpha$ will be considered statistically significant.

Summary statistics will consist of the number and percentage of responses in each category for discrete variables, and the mean, median, standard deviation (SD), minimum, and maximum for continuous variables.

All mean and median values will be formatted to one more decimal place than the measured value. Standard deviation values will be formatted to two more decimal places than the measured value.

All percentages will be rounded to one decimal place. The number and percentage of responses will be presented in the form XX (XX.X), where the percentage is in the parentheses. The decimal of the percentage may be dropped due to space constraints when creating a table.

All listings will be sorted for presentation in order of intervention group, site number, subject number, and date of procedure or event.

All analysis and summary tables will have the population sample size for each intervention group in the column heading.

Calculating change from baseline to a visit will be done as follows: change = visit – baseline.

Unless otherwise specified, baseline is defined as the last data point before the participant is randomized.

Version 9.4 of SAS® or higher will be the statistical software package used to produce all summaries, listings, statistical analyses, and graphs.

Updated version of MedDRA will be used for adverse event and pre-intervention coding.

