7.1. Primary Endpoint Analysis

The primary study endpoint will be a composite outcome of all-cause mortality, MI, coronary revascularization, acute renal failure, or post-randomization stroke within 90 days from randomization. A clinical events committee will adjudicate all component events for the primary endpoint. The number and percentage of participants with the composite endpoint at the 90-day visit after the randomization will be summarized and compared according to assigned transfusion strategy (analysis by intent to treat) using Pearson χ^2 test. Another analysis will compare primary endpoint between the two transfusion strategies stratified by clinical sites using the Cochran-Mantel-Haenszel test (Table 16a-e). The test for differences between transfusion strategies in the primary outcome will be conducted at an overall α -level of 0.05. Additional analysis will be conducted using logistic models to adjust for other clinical factors, such as age, RCRI, and nadir Hb. The interactions of the intervention with age, RCRI and nadir Hb will also be considered.

Odds ratio and 95% confidence interval (CI) will be presented using SAS PROC GENMOD or PROC LOGISTIC. Assumptions of the model including linearity in the logit of the composite event risk for continuous variables will be checked. We will assess goodness-of-fit using the statistic -2 log likelihood, which has a chi-square distribution under the null hypothesis that all the explanatory variables in the model are not associated with the outcome

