7.3. Tertiary endpoint Analyses

Tertiary endpoints included in the analysis are individual components of the primary composite outcome of all-cause mortality, MI, coronary revascularization, acute renal failure, or post-randomization stroke at 90 days. All are considered as binary variables in the study, and the effect of transfusion strategy on these endpoints will be analyzed initially with a Pearson chi-square test (Tables 22a-e). The test for differences between transfusion strategies in each tertiary outcome will be conducted at an α -level of 0.01. Additional analyses will be carried out by taking account of age, RCRI, and nadir Hb using logistic regressions (Tables 23a-e), as stated in the secondary endpoint analyses. The analyses will be done in the ITT, mITT, No-Recent-Transfusion, Completers, and Per Protocol populations.

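### The fixed 0.01 level for each of the five secondary endpoints is valid, but Holm's procedure at family-wise 0.05 would never reject less and gains power if several effects are real

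*SAP*

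**What the plan says.** SAP 3.2.2 states: "There are five secondary outcome measures based on their use in previous studies". They are infectious complications at 90 days, cardiac complications other than MI at 90 days, one-year mortality, the 30-day composite, and length of stay.

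The decision rule in SAP 7.2 is "The test for differences between transfusion strategies in each secondary outcome will be conducted at an" alpha level of 0.01, and protocol XVI.E.3 has the same rule. SAP 5.3 makes it two-sided: "Two-tailed tests will be performed for all analyses that use statistical testing". No ordered, step-down or gatekeeping procedure appears for these endpoints.

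For the primary endpoint, SAP 7.1 says "The test for differences between transfusion strategies in the primary outcome will be conducted at an overall" alpha level of 0.05. The five components of the primary endpoint form a separate tertiary set under SAP 7.3, again at 0.01 each: "The test for differences between transfusion strategies in each tertiary outcome will be conducted at an" alpha level of 0.01 (also protocol XVI.E.4). The table shells show 99% intervals for the secondary and tertiary logistic models and the secondary Cox models (SAP Tables 19, 23 and 28).

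**The concern.** When five tests share a 5% error budget, giving each a fixed fifth of it is the simplest valid choice but not the most efficient. Once one hypothesis has been rejected at 0.01, the rest can be tested at a less strict level without the family error exceeding 5%. The fixed rule does not use this.

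It could matter here because all five secondary hypotheses (protocol IV.B, SAP 3.1) predict benefit from the liberal strategy, and a step-down rule helps most when several effects are real. The endpoints also overlap: a death by day 30 counts in both the 30-day composite and one-year mortality. Any replacement must therefore be valid under dependence, and Holm's procedure is.

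At stake is how many real secondary effects are declared. The primary analysis is not touched.

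**Working it through.** **Inputs from the documents.** Five secondary endpoints (SAP 3.2.2), each at two-sided 0.01 (SAP 7.2 and 5.3; protocol XVI.E.3).

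**Inputs that must be assumed.** The only effect size in the documents is for the primary composite: "a baseline event rate of 30% for the composite endpoint is expected in the restrictive group" and "We also assume a 25% reduction or 22.5% event rate in the liberal group" (SAP 4.5). No secondary rates or effects are given. I therefore took marginal power of 50%, 80% and 90% at two-sided 0.05, and an equal correlation of 0, 0.3 or 0.5 between the test statistics.

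**1. The level in the plan.** 0.05 / 5 = 0.01, so the five tests together spend 5 × 0.01 = 0.05. If they were independent, the chance of any false rejection would be 1 − 0.99^5 = 0.0490.

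**2. Holm's thresholds.** Order the p-values from smallest to largest. Compare the j-th with 0.05 / (5 − j + 1), giving 0.01, 0.0125, 0.0167, 0.025 and 0.05, and stop at the first failure. The first threshold is the plan's own level and the others are larger. So every endpoint rejected at 0.01 is also rejected by Holm, and the chance of at least one rejection is the same under both rules.

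**3. Power at the fixed 0.01.** An endpoint with a given power at 0.05 has expected z = 1.960 + z(power). Its power at 0.01 is Φ(expected z − 2.576), ignoring the far tail.
- 50%: Φ(1.960 − 2.576) = 0.27
- 80%: Φ(2.802 − 2.576) = 0.59
- 90%: Φ(3.242 − 2.576) = 0.75

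**4. Fixed 0.01 against Holm.** Simulation of five equally correlated normal statistics, 400,000 draws per setting. Entries are average power per real effect; ranges are over correlation 0 to 0.5.

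| Power at 0.05 | Fixed 0.01 | Holm, 1 real | Holm, 2 real | Holm, 3 real | Holm, 5 real |
|---|---|---|---|---|---|
| 50% | 27% | 27% | 28% | 28–29% | 31–33% |
| 80% | 59% | 59% | 61% | 63% | 69–70% |
| 90% | 75% | 75% | 76–77% | 78–79% | 84–86% |

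Before rounding, the gains are at most 0.1 points with one real effect, 0.8 to 1.9 with two, 1.6 to 4.2 with three and 3.9 to 11.5 with five. With five real effects at 80% each, the chance of declaring all five rises from 7% to 29% at correlation 0, and from 24% to 48% at correlation 0.5. In no draw did the fixed rule reject a hypothesis that Holm kept.

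**5. Family error.** With all five nulls true, the two rules have identical error: 4.9%, 4.6% and 4.2% at correlation 0, 0.3 and 0.5. With some effects real, Holm's error on the remaining nulls is higher than the fixed rule's (3.4% against 1.9% with three real effects at 80% and correlation 0). It never exceeded 4.7%.

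**6. Tertiary set.** Here the documents do give rates. Protocol Table 2 (nadir Hb 6–9 gm/dl) has death 15.3%, MI 11.0%, acute renal failure 11.1% and revascularization 0.4%; protocol section II puts stroke at about 1%. Assume a 25% relative reduction in each component and 1444 / 2 = 722 per arm. For death, z = (0.153 − 0.11475) / √[(0.153 × 0.847 + 0.11475 × 0.88525) / 722] = 2.14, so power at 0.01 is Φ(2.14 − 2.576) = 33%. Holm raises this to 35%. MI goes from 21% to about 23%. Over all components, correlation 0 to 0.5, and 722 or 760 per arm, the gain is 0.3 to 2.5 points.

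**The case against.** The strongest reply is that nothing is wrong. A fixed 0.01 is pre-specified, valid under any dependence, and the same in both documents. That stands: choosing Holm is a gain in efficiency, not the repair of an error.

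A reader might infer that the sponsor adopted Bonferroni at a 5% family level. The documents do not support that as a statement of intent. Neither names the method or the family total, and protocol XVI.E.5 also uses 0.01 for the age-of-blood analyses, which have three outcomes (3 × 0.01 = 0.03). The level may simply be a stricter threshold for non-primary analyses. Only the arithmetic is certain.

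A reader might also take the drop from 80% to 59% as what Holm would recover. It is not. That drop compares 0.01 with no adjustment at all, and Holm reaches at best 69–70% in that setting, with all five effects real. The protocol's own background gives reason to doubt five benefits: section I cites a cardiac-surgery trial in which units transfused predicted infectious and cardiac complications, and section XI.E lists heart failure from fluid overload as a transfusion risk.

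Agreement between test and interval is a fair argument for the fixed level. SAP 7.1 treats a logistic effect as significant when its interval excludes 1, and SAP 7.2 carries that approach over. Holm breaks the match with the 99% intervals beyond its first step. This is a real cost, but a manageable one if the intervals are labelled descriptive.

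Finally, replacing 0.01 by Holm is not enough by itself. Each binary endpoint also has logistic, log-rank and Cox analyses, and every analysis is repeated in five populations (SAP 7.2 and 7.4). The plan must say which p-value enters the procedure. The fix below does so.

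**Conclusion.** The point holds as an inexpensive improvement. The fixed 0.01 rule is valid. Holm at family-wise 0.05 has the same error guarantee under any dependence and never rejects less. That comparison is a mathematical fact and needs no assumption about this trial.

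The size of the gain does rest on assumptions, because the documents give no secondary effects. At 50–90% marginal power and correlation 0 to 0.5, it is about 0 points per real effect with one real effect, 1 to 2 with two, 2 to 4 with three and 4 to 12 with all five. The upper figures need every secondary hypothesis to be true and well powered.

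The 5% applies to the secondary set alone, with one test per endpoint in one population. Neither rule covers the secondary and tertiary sets jointly. For the tertiary components the gain is too small to press.

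**What to change.** Before outcome data by arm are seen, amend SAP 7.2 and protocol XVI.E.3 as follows.

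- The confirmatory secondary family is the unadjusted ITT test of each endpoint: Pearson chi-square for the four binary endpoints and Wilcoxon rank sum for length of stay.
- These five p-values are tested by Holm's procedure at family-wise 0.05, two-sided.
- The adjusted models, the time-to-event analyses and the analyses in the other populations are supportive.
- The 99% intervals are descriptive and do not define significance.

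Extending this to the tertiary components is optional. It would need matching edits to SAP 7.3 and protocol XVI.E.4.

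**Cost.** A short text change in two documents, table footnotes and one programming step; no extra participants, visits or data. The downside is that an endpoint declared significant by Holm may have a 99% interval that includes the null, and the report should say so. The timing is essential: choosing Holm after seeing results by arm would not be credible.
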